## 3. Analysis of secondary outcomes.

Primary analysis of other time to event outcomes will be performed using unadjusted log rank tests that have associated Kaplan-Meier plots, similar to the primary analysis of the primary study outcome. Secondary analysis of these outcomes will use Cox regression to adjust for baseline subject factors (covariates) that are known to be associated with the outcome.

The primary analyses of changes in continuous measures such as absolute and percent changes in spirometry and dyspnea scores, for example, will be analyzed using an analysis of covariance where change from baseline to a particular time period is the dependent variable.

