## Table1. Readmission rates following COPD Hospitalization

Dinesen et al 2012	Prospective	~5%	~6%	~10%

The rate of 30 day readmissions in these reports varies from 5-34% with the majority of studies suggesting that approximately 15% suffer such an event in that time frame. This readmission rate increases further by 60 days (6-30%) and 90 days (10-40%).Data from the AHRQ using the HCUP database found that 20.5% of U.S. COPD patients were readmitted within 30 days and that 85% of these included COPD as the primary or secondary diagnosis).{{1159 Elixhauser,A. 2011}} A summary of published literature suggests that readmissions are frequently seen in this population.

Survival is another extremely relevant endpoint to study the effect of an intervention during COPD hospitalization. The Study to Understand Prognosis and Preferences for Outcomes and Rates of Treatment (SUPPORT enrolled patients admitted with COPD exacerbations and reported an in-hospital mortality of 11% in patients presenting with acute hypercapneic respiratory failure.{{1152 Connors,A.F.,Jr 1996}} The 180 day mortality was 33% and the 2-year mortality was 49%. Several

other studies have reported in-hospital mortality rates of 11-24% and 22-35% after one and two year's follow-up respectively (Figure 2). The 2010 PHC4 dataset reports the average inpatient mortality rate for COPD readmissions to be 3.9%, but ranges from non-complicated readmission mortality rates of 1.45 % to 5.0% if pneumonia is the cause of readmission in a patient initially admitted with COPD or even higher at 11.6% mortality if respiratory failure is the cause for readmission.

These data demonstrate that readmission and survival following COPD hospitalization are clinical relevant and meaningful endpoints that occur with increased frequency following the index hospitalization.

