## Outcomes:

In this pilot proposal, 100 patients at three centers will be evaluated to test the feasibility of conducting this study and to assess the treatment effect of roflumilast to be able to power an appropriate definitive phase III multicenter trial. Our ultimate aims of the phase III trial will be:

**1) Primary**: time to all-cause mortality or re-hospitalization during the 180 days postrandomization. **2) Secondary:** respiratory death or respiratory re-hospitalization during the 180 days post-randomization; rate of death or readmission during the 30 days postdischarge; treatment failure (see definition below); change in health status, FEV1, and dyspnea during the 180 days post-randomization; length of hospital stay during the index hospitalization. **3) Other: assess tolerance of roflumilast vs. placebo in hospitalized AECOPD.** 

[figure not shown]

Figure 4 shows the overall study design, proposed study measurements, and time points for assessment. Patients hospitalized with AECOPD will be eligible for enrollment during their hospitalization with treatment being started before discharge from the hospital.. Demographics, blood tests, health related quality of life, comorbidity (Deyo-Charlson index), post bronchodilator spirometry, vital signs, dyspnea measured by MMRC, SaO2 and amount of inspired O2 to maintain SaO2> 90% at rest, serum fibrinogen levels, HBA1c, Biomarkers and Genetics will be obtained after enrollment and then patients will be randomized to standard AECOPD care plus roflumilast 500 ug daily vs. placebo. Patients will begin roflumilast or placebo  $\leq$  12 hours of hospitalization for a total period of 180 days post enrollment. On discharge day (approximately day 3-4 after admission based on the recent COPD CRN zileuton study of hospitalized AECOPD), the measurements will be repeated as indicated (baseline measurements), with follow-up phone assessments at days 7, 30, 60, 90, 120 and 194 days post enrollment. An inperson clinical visit will be conducted at days 14 and 180 post randomization.

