## 4. N. Contraindications and side effects to the use of Roflumilast.

**1. Contraindications**: Roflumilast in contraindicated in patients with moderate or severe liver impairment (Child-Pugh class B and C)

2. Side effects: Adverse events experienced by > 3% of patients in clinical trials of roflumilast included diarrhea (9.5%), weight loss (7.5%), nausea (4.7%), headache (4.4%) and back pain (3.2%). Patients discontinued therapy due to adverse effects more frequently with roflumilast (14.8%) compared to placebo (9.9%). Diarrhea and nausea were the most common adverse reactions leading to drug discontinuation in prior trials. Serious adverse events that occurred more frequently with roflumilast compared to placebo included diarrhea, atrial fibrillation, lung cancer, prostate cancer, acute pancreatitis acute renal failure. Less common adverse events, (1-2%) of patients that were more frequently reported with roflumilast use as compared to placebo included abdominal pain, anxiety, heartburn, depression, gastritis, rhinitis, sinusitis, muscle spasms, tremor, urinary tract infection, and vomiting. Roflumilast carries a warning for increased psychiatric adverse events and suicidality. Patient should be monitored for changes in mood including worsening insomnia, anxiety or depression or suicidal ideations. Roflumilast also carries a warning for weight loss. 20% of patients may experience moderate weight loss between 5 to 10% of ideal body weight compared to 7% with placebo.

Roflumilast side effects reported in  $\ge 2\%$  of recipients from 8 clinical trials as listed in the manufacturer's package insert are listed in the table below.

Treated with Roflumilast 500 mcg daily and Greater Than Placebo Treatment		
Adverse Reactions	Roflumilast	Placebo
(Preferred Term)	(N=4438)	(N=4192)
	n (%)	n (%)
Diarrhea	420 (9.5)	113 (2.7)
Weight decreased	331 (7.5)	89 (2.1)
Nausea	209 (4.7)	60 (1.4)
Headache	195 (4.4)	87 (2.1)
Back pain	142 (3.2)	92 (2.2)
Influenza	124 (2.8)	112 (2.7)
Insomnia	105 (2.4)	41 (1.0)
Dizziness	92 (2.1)	45 (1.1)

Decreased appetite	91 (2.1)	15 (0.4)

Other side effects reported in 1- 2% of recipients include: Gastrointestinal disorders (abdominal pain, dyspepsia, gastritis, vomiting); Infections and infestations (rhinitis, sinusitis, urinary tract infection); Musculoskeletal and connective tissue disorders (muscle spasms); Nervous system disorders (tremor); and Psychiatric disorders (anxiety, depression).

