## 4. R. Statistical analysis plan.

The primary analysis for all study outcomes will be performed on an intention to treat basis. In the intention to treat approach, all subjects are analyzed in the group to which they were randomized, regardless of whether the assigned treatment was adhered to and regardless of whether there were any eligibility violations.

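### The ANCOVA on change can include only patients alive and measured at the visit, and the plan has no rule for deaths or missed visits, so at day 180 it falls short of the promised all-subjects ITT analysis.

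*Combined protocol and SAP*

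**What the plan says.** Section 4.R opens with a commitment that covers every endpoint: "The primary analysis for all study outcomes will be performed on an intention to treat basis". It then defines the term: "all subjects are analyzed in the group to which they were randomized, regardless of whether the assigned treatment was adhered to".

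Section 4.R.3 covers "changes in continuous measures such as absolute and percent changes in spirometry and dyspnea scores, for example", and the method for these is an ANCOVA in which "change from baseline to a particular time period is the dependent variable". Health status is not named there. It belongs to the same class, and the Outcomes section lists it beside the other two: "change in health status, FEV 1 , and dyspnea during the 180 days post-randomization".

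The schedule (Outcomes, 4.B and 4.D) gives SGRQ, EQ-5D and mMRC at clinic visits on days 14 and 180. Spirometry is done at enrolment, at discharge and at day 180, so day 180 is the only FEV1 after discharge.

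The text has no imputation method, no repeated-measures model, no rule for a patient who dies before the visit, and no sensitivity analysis for missing values. Its one rule for lost patients is the censoring rule in 4.R.2, which applies to the time-to-event endpoint.

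**The concern.** A change score exists only for someone who is alive and assessed. Nothing in the plan fills the gap for anyone else, so the method as written cannot deliver the all-subjects analysis that 4.R promises.

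This matters more here than in most trials because death is a component of the primary endpoint and the hypothesis is that the drug reduces it. If it does, and if the patients kept alive would have had worse FEV1, dyspnea or health status than other survivors, the treated arm's survivors look worse on average and the comparison is biased against the drug. Missed visits could push the result in either direction.

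The pilot exists to inform a phase III design, and 4.R.4 says these same endpoints will be secondary outcomes there. Survivor-only estimates reported as ITT would feed into that design.

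**Working it through.** **The plan's own figure.** The documents give no SD, power, sample size or dropout rate for the continuous outcomes. The only design calculation is for the primary endpoint: 73 events, hazard ratio 1.654, two-sided alpha 0.10, power 0.70. Schoenfeld's formula gives 4 × (1.645 + 0.524)² / (ln 1.654)² = 74.3, rounded up to 75, and 73 events give power 0.693. The figure reproduces, but it does not bear on this point.

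**Inputs.**
- N = 100 (4.R.4). An equal split of 50 per arm is assumed, because the ratio is not stated.
- Mortality: 33% at 180 days is the background figure in 1.B ("The 180 day mortality was 33% and the 2-year mortality was 49"). It comes from patients with acute hypercapnic respiratory failure and is used only as an upper bound. Rates of 10%, 15%, 20% and 25% are assumptions.
- Missed day-180 visits among survivors: 10-15%, assumed.
- SGRQ change: SD 15, assumed. Correlation r between death and latent worsening: 0.3 to 0.6, assumed.

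**Patients with a day-180 value** = 100 × (1 − mortality) × (1 − missed visits).
- 10% mortality: 100 × 0.90 × 0.90 = 81; 100 × 0.90 × 0.85 = 76.5.
- 33% mortality: 100 × 0.67 × 0.90 = 60.3; 100 × 0.67 × 0.85 = 57.0.

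**Precision.** The detectable standardized difference at the plan's alpha and power is (1.645 + 0.524) × √(4/n). It is 0.43 at n = 100 and 0.57 at n = 57.

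**Bias with no true effect.** Let latent worsening be normal with SD 15, and let death occur when a second normal variable, correlated r with it, exceeds its (1 − p) quantile z. The survivors' mean is then −15 × r × φ(z)/(1 − p). The bias is the difference between arms: 15 × r × [φ(z_c)/(1 − p_c) − φ(z_t)/(1 − p_t)], where c is control and t is treated. The ratio φ(z)/(1 − p) is 0.5405 at 33% deaths, 0.4237 at 25%, 0.3500 at 20%, 0.2743 at 15% and 0.1950 at 10%.

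| Deaths, control vs treated | Difference in ratio | Bias, r = 0.3 | Bias, r = 0.6 |
|---|---|---|---|
| 15% vs 10% | 0.0793 | 0.36 | 0.71 |
| 33% vs 25% | 0.1168 | 0.53 | 1.05 |
| 33% vs 20% | 0.1905 | 0.86 | 1.72 |

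The largest value is 1.72/15 = 0.11 SD.

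**Bias against sampling error.** Take 12.5% missed visits (assumed).
- 15% vs 10% deaths: 37.2 and 39.4 patients are analysed. The standard error is 15 × √(1/37.2 + 1/39.4) = 3.43, so the bias is 0.10 to 0.21 standard errors. The two-sided 10% error rate becomes 10.2% to 10.7%.
- 33% vs 20% deaths, r = 0.6: 29.3 and 35.0 patients are analysed. The standard error is 3.76, the bias is 0.46 standard errors, and the error rate becomes 13.5%.

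**The case against.** The strongest reply is that the plan is silent, not wrong. A reader might infer that it orders patients to be dropped, but no section says so. ITT in 4.R is defined by assigned group, adherence and eligibility, and ANCOVA with pre-specified imputation would fit both sections for survivors who miss the visit. This stands as a limit on wording: exclusion is the default result of having no rule. It does not remove the gap, because no rule is given and a value after death is not an ordinary missing value.

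A reader might also infer that the day-14 questionnaires and the discharge FEV1 go unused. The text does not support that. The time period in 4.R.3 is generic and allows an analysis at each visit. Day 180 is the focus here because the endpoints run over 180 days and losses are greatest then.

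A third tempting step is to take the discontinuation figures in 4.N ("Patients discontinued therapy due to adverse effects more frequently with roflumilast (14.8%) compared to placebo (9.9") as evidence of unequal dropout. Those are stops of therapy in earlier trials, and 4.P.1 expects patients permanently off drug to stay in follow-up for outcomes. The documents give no missed-visit rate for either arm.

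The 33% mortality also fits this trial poorly. If times are exponential, the 8-month median in 4.R.4 implies 1 − 2^(−6/8) = 41% with death or readmission by six months. Deaths at 33% would leave little room for readmissions, so the low-mortality rows of the table are the more plausible ones.

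Finally, these are secondary outcomes in a pilot, and the likely bias is small against its standard error. That is fair and limits the weight of the point.

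**Conclusion.** The point holds in this form: 4.R promises all subjects, 4.R.3 names a method that can use only those alive and measured, and nothing in the plan covers deaths or missed visits. At day 180 the analysis would rest on roughly 76 to 81 of 100 patients under assumed 10% mortality and 10-15% missed visits, and on 57 to 60 at the upper-bound mortality.

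The bias from deaths is likely modest, at about 0.4 to 0.7 SGRQ points for 15% versus 10% deaths and at most 1.7 in the extreme case. It rests on the assumed SD, correlation and death rates, and on the assumption that patients saved from death would have had worse scores. If death were unrelated to the latent score there would be no such bias, but the analysis would still not include all subjects.

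ANCOVA itself is a legitimate method. The defect is its use under an all-subjects label with no rule for patients who have no value. The change should be made, but the primary log-rank analysis does not depend on it.

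**What to change.** Amend 4.R.3 as follows.

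1. **Deaths.** Pre-specify a companion rank analysis at day 180 for FEV1, dyspnea and health status, with deaths ranked worst. State how a survivor with no day-180 value enters the ranking. This is the part that addresses deaths, because a mixed model alone implicitly extrapolates values beyond death.
2. **Missed visits among survivors.** Use a mixed model on the post-baseline values already collected: days 14 and 180 for SGRQ, EQ-5D and mMRC. Include the baseline value and center, which is the randomization stratum, as covariates. For FEV1, the discharge value can enter only after the Outcomes section is reconciled, because it labels the discharge-day assessments as baseline measurements. Until then FEV1 has a single follow-up value, so a mixed model gains nothing over ANCOVA.
3. **Labelling and reporting.** Describe any ANCOVA as an analysis of survivors with data, and report deaths and missing values by arm at each visit.

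The cost is SAP wording and a few extra model runs, with no new data collection. The downside is a second result on a rank scale that has to be explained beside the first.

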## 4. Assessment of treatment effect

In this pilot proposal, the treatment effect of roflumilast vs. placebo to prolong the time to event of a combined endpoint of death or re-hospitalization will be assessed in an intention to treat manner. In a similar manner, the treatment effect of roflumilast vs. placebo to effect all of the secondary endpoints proposed to be measured in the pivotal phase III trial will also be measured (time to respiratory death or respiratory re-hospitalization during the 180 days post-randomization; rate of death or readmission at 30 days post-discharge; treatment failure [see definition below]; change in health status, change in FEV1, and dyspnea during the 180 days post-randomization; length of hospital stay during the index hospitalization; and the tolerance of roflumilast vs. placebo in hospitalized AECOPD).

Because this is a pilot study the intent is to see if there is a signal that would justify a larger clinical trial. Therefore the significance level has been set to 0.1 and the power has been set at 0.7. A total of 100 patients will enter this two treatment parallel-design study. The probability is 70 percent that the study will detect a treatment difference at a two sided 10.0 percent significance level, if the true hazard ratio is 1.654. This is based on the assumption that the accrual period will be 36 months and the follow up period will be 6 months and the median time to event is 8 months. The total number of events will be 73.

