## 4. Methods:

**4. A. Study Population.** 100 AECOPD patients hospitalized at Temple University Hospital, Temple University Episcopal Hospital Campus, Jeanes Hospital and St Mary's Hospital.

**Inclusion Criteria.** Primary diagnosis of AECOPD defined as acute increase in dyspnea, sputum volume, and/or sputum purulence without other identified cause; consent obtained and treatment started before discharge from the hospital ; patient age >40, < 80 years old; cigarette smoking  $\geq$  10 pack-years; informed written consent.

**Exclusion Criteria.** Prior diagnosis or high suspicion for asthma based on investigator judgment; pulmonary edema, pneumonia, interstitial lung disease or significant Version 04.13.2015

bronchiectasis based on admission chest x-ray; intubated and mechanically ventilated at the time of evaluation; active liver disease, or transaminase elevations ( $\geq$  3xULN); history of alcoholism or heavy ethanol use; history of suicidal behavior  $\leq$  2 years or suicidal ideation  $\leq$  6 months prior to enrollment; pregnant or lactating females. Those on the following excluded medications: P450 inducers (e.g., rifampicin, phenobarbital, carbamazepine, and phenytoin) and CYP3A4 inhibitors or dual inhibitors that inhibit both CYP3A4 and CYP1A2 simultaneously (e.g., erythromycin, ketoconazole, fluvoxamine, enoxacin, cimetidine.

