## 4. B. Study Procedure

Study will begin before patient's discharge from the hospital and last for 194 days.

Baseline: Will occur during the duration of admission stay in the hospital. Patients will have a medical history taken as well as smoking history. Patients will also be given a physical exam including vital signs. A spirometry test will also be performed. Women with the potential to become pregnant will be given a pregnancy test. Data will also be collected in regards to dyspnea scales, Deyo-Charlson index, and GOLD classification. Patients will complete a Columbia Suicide Severity Rating Scale to exclude patients with a history of suicidal behavior  $\leq 2$  years or suicidal ideation  $\leq 6$  months prior to enrollment Randomization: Patients who are eligible to enroll in this study will be randomized to one of two treatment groups. Randomization will be done using a randomized block design stratified by treatment center. One group will receive rollumilast 500 mcg (Daliresp®) and the other will receive a placebo tablet. Patients will begin one of these treatment arms prior to hospital discharge for a total period of 180 days post enrollment.

Day of hospital discharge: A spirometry test will be performed and an adverse event assessment will be completed.

Day 7: Phone Visit. Data to be collected includes: interim history, adverse events assessments, vital status, and exacerbation history. During this telephone visit the study doctor or nurse coordinator will ask how the patient is feeling and if they have needed to visit the doctor or go to the emergency room or hospital since the last time they were contacted. They will be asked how well they are tolerating the study drug.

Day 14: Clinic Visit. At this visit vital signs, C-SSRS test, interim history, adverse event assessment, vital status, and exacerbation history will be recorded. The following questionnaires will given: EQ-5D, the St. George's Respiratory Questionnaire (SGRQ), and the Modified Medical Research Council dyspnea score (MMRC).

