## 1. Analysis of baseline characteristics.

Univariate descriptive statistics will be calculated for baseline parameters overall and by treatment group. For categorical outcomes, these will include the number percentage of subjects in each category. For continuous variables, these will include the mean and standard deviation for variables with approximately normal distributions and the median and 25th and 75% percentiles for variables with skewed distributions.

**2.** Analysis of the primary endpoint. The primary outcome is time from randomization to a composite outcome of all cause re-hospitalization and all-cause mortality, whichever comes first. The primary analysis will be a log-ranked test and associated Kaplan-Meier plot, unadjusted for any covariates. Censoring will occur at the earliest date of any of the following occurrences, unless the subject has already experienced the primary outcome event:

• Lost to follow-up despite intensive efforts

- Subject or healthcare proxy withdrawal of consent
- 180 days after randomization.

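### Do the 30-day post-discharge rate and the respiratory composite need a written rule for deaths that their definitions do not cover?

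*Combined protocol and SAP*

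**What the plan says.** Section 4.B puts the start of treatment inside the index stay: "Patients will begin one of these treatment arms prior to hospital discharge". The inclusion criteria in section 4.A agree: "consent obtained and treatment started before discharge from the hospital". Section 4.R opens with "The primary analysis for all study outcomes will be performed on an intention to treat basis" and explains that "all subjects are analyzed in the group to which they were randomized".

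The 30-day endpoint is tied to discharge. The Outcomes part of section 3.B has "rate of death or readmission during the 30 days postdischarge", and section 4.R item 4 has "rate of death or readmission at 30 days post-discharge".

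The respiratory composite runs for 180 days from randomization. Section 4.R item 3 gives secondary time-to-event outcomes an unadjusted log-rank test and a Kaplan-Meier plot, "similar to the primary analysis of the primary study outcome". The only censoring rule is in item 2 and is written for the primary endpoint: "Censoring will occur at the earliest date of any of the following occurrences, unless the subject has already experienced the primary outcome event". Its list holds loss to follow-up, withdrawal of consent and day 180. Death is not on it, because every death is a primary event.

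Index-stay deaths are counted in two other places: the primary composite, which starts at randomization (4.R item 2), and treatment failure (4.F), which includes death from any cause during the initial stay.

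**The concern.** For the 30-day endpoint, the randomized set and the post-discharge window do not fit together. A patient who dies before discharge is in the denominator but has no window in which to have an event. On one strict reading the patient is event-free, so a death counts as a good result in an endpoint that names death. Dropping the patient departs from intention to treat and compares only those who survived to discharge.

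For the respiratory composite, the primary censoring list is carried over to an endpoint where some deaths are not events. If non-respiratory deaths are censored, one minus Kaplan-Meier overstates absolute risk. If those patients stay at risk to day 180 the curve is right, but the log-rank test is no longer cause-specific. The plan does not choose.

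At stake would be two secondary estimates in a pilot meant to inform a phase III trial, under a scoring rule that might be picked after the deaths are known.

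**Working it through.** The plan gives no figure for either endpoint. Its one design figure, 73 events, belongs to the primary endpoint and does not enter here.

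**30-day endpoint: inputs**

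- n = 50 per arm: 100 patients (4.R item 4), equal allocation assumed.
- d, mortality between randomization and discharge: 1.45% and 3.9%. These are inpatient mortality figures for COPD readmissions in section 1.B, used as stand-ins. They are probably high, because enrolment can happen at any time before discharge and section 4.A excludes intubated patients and those with pneumonia or pulmonary edema.
- e, 30-day event rate in patients discharged alive: 15% and 20.5%, from section 1.B. These are readmission rates only; no 30-day death-or-readmission rate is given.

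**Rate under each scoring rule**

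- Event-free: (1 − d)e
- Dropped: e
- Counted as events: d + (1 − d)e

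| d | e | Deaths per arm (50d) | Event-free | Dropped | Counted | Counted − dropped = d(1 − e) |
|---|---|---|---|---|---|---|
| 1.45% | 15% | 0.7 | 14.8% | 15.0% | 16.2% | 1.23 points |
| 1.45% | 20.5% | 0.7 | 20.2% | 20.5% | 21.7% | 1.15 points |
| 3.9% | 15% | 1.95 | 14.4% | 15.0% | 18.3% | 3.32 points |
| 3.9% | 20.5% | 1.95 | 19.7% | 20.5% | 23.6% | 3.10 points |

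The standard error per arm is √(e(1 − e)/50): √(0.15 × 0.85/50) = 5.05 points and √(0.205 × 0.795/50) = 5.71 points.

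**Difference between arms**

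If d is equal in both arms, the expected difference is (1 − d)(e₁ − e₂) whether deaths are event-free or counted, and e₁ − e₂ if they are dropped. The rule therefore multiplies the expected difference by 1 − d at most: 0.9855 or 0.961.

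In a single trial the rule matters more. Each unbalanced index-stay death moves the difference by 1/50 = 2.0 points between event-free and counted scoring. The standard error of the difference at d = 1.45%, deaths counted, is 7.4 to 8.2 points.

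**Test decisions**

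I used 400,000 simulated trials per setting, equal d and e in both arms, and a pooled z test at two-sided 10%. The test is my assumption, since the plan names none for this rate.

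- Event-free and counted scoring disagree in 4.5% to 4.9% of trials at d = 1.45%, and in 7.6% to 8.2% at 3.9%.
- At an assumed d = 0.5% they disagree in 2.1% to 2.2%.
- At the two stand-in values, each rule rejects in 9.6% to 10.3% of trials, so none inflates the false-positive rate materially.

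**Respiratory composite**

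The documents give no risks for this endpoint, so all inputs are assumed. Let F₁ be the 180-day respiratory incidence and F₂ the incidence of non-respiratory death occurring first, with constant hazards. Then H₁ = −ln(1 − F₁ − F₂) × F₁/(F₁ + F₂), and one minus Kaplan-Meier with such deaths censored is 1 − exp(−H₁).

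- F₁ = 30%, F₂ = 5%: H₁ = 0.4308 × 0.30/0.35 = 0.3692, giving 30.9%, an excess of 0.9 points.
- F₁ = 30%, F₂ = 10%: H₁ = 0.5108 × 0.75 = 0.3831, giving 31.8%, an excess of 1.8 points.
- Range for F₂ from 5% to 10%: excess 0.6 to 1.2 points at F₁ = 20%, and 1.2 to 2.6 points at F₁ = 40%.
- Standard error at n = 50: √(0.30 × 0.70/50) = 6.5 points.
- Between arms, 30% against 20% with F₂ = 10% in each: 31.83 − 21.16 = 10.66 points instead of 10.00, with a standard error of √((0.21 + 0.16)/50) = 8.6 points.

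If the item 2 list is followed to the letter, non-respiratory deaths are not censored, the patients stay at risk to day 180, and the excess is zero.

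**The case for a change.** The best case for acting is that the question will probably arise and is cheap to settle now. With the same stand-ins, the chance of at least one index-stay death among 100 patients is 1 − 0.9855¹⁰⁰ = 77%, or 1 − 0.961¹⁰⁰ = 98%. An uneven split can show: with 5 deaths against 1 and e = 15% in both arms, the difference is −1.2 points if deaths are event-free, 0 if dropped and +6.8 if counted. Event-free scoring then slightly favours the arm with more early deaths. Two sentences would prevent a choice made after the data are seen, and phase III lists the same secondary endpoints.

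What stands is that both rules are unwritten and that a single trial's 30-day difference can move by a few points. The rest is weaker:

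- No sentence scores the dead patient as event-free. The text is silent, and the item 4 wording can equally be read as status at day 30, with a dead patient counted as dead.
- Phase III is to be powered on its primary endpoint, time to death or re-hospitalization from randomization, which neither gap touches. No decision is attached to either secondary endpoint.
- Counting index-stay deaths as events would do more than clarify. It would turn a post-discharge rate into a composite from randomization to 30 days after discharge, no longer directly comparable with published readmission rates and overlapping two endpoints that already include those deaths.
- Censoring at non-respiratory death is the usual default for the respiratory composite. Under it the log-rank test is already cause-specific, and a cumulative incidence plot would change only the curve.

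**Conclusion.** No change follows. The plan leaves two scoring details unstated for secondary endpoints of a 100-patient pilot, and analysts can fill them sensibly when they program the analysis.

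For the 30-day rate, counting rather than dropping index-stay deaths adds about 1.2 points at 1.45% early mortality and 3.1 to 3.3 points at 3.9%, less than one standard error of an arm in either case. For the respiratory composite, the curve is either correct or 0.9 to 1.8 points high, against a standard error of 6.5.

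These sizes rest on stand-in mortality figures that are probably too high, on assumed respiratory risks, and on equal early mortality in the two arms. If treatment did change index-stay mortality, the 30-day rules would measure different things. That effect would still be counted in the primary endpoint and in treatment failure, and is not lost.

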## 4. Q. Assessment of effectiveness.

The present proposal is a pilot study designed to test the feasibility of a future project to be conducted in a multicenter trial in hospitalized patients, to determine the tolerance of roflumilast in hospitalized COPD patients, and to determine the treatment effect of roflumilast to decrease all-cause mortality and all cause readmission rate as add-on therapy. The specifics aims will be:

- 1. Determine the tolerance of roflumilast in hospitalized COPD patients
- 2. Determine the treatment effect of roflumilast as add-on therapy to decrease all cause readmission and mortality as a composite endpoint 180 days after randomization to roflumilast or matching placebo ≤ 12 hours after hospitalization for acute COPD exacerbation.

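### The 73 events and 70% power cannot arise under 180-day censoring; on the reading that reproduces them, the design gives about 33 events and 42% power

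*Combined protocol and SAP*

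**What the plan says.** Section 4.R, item 4 (Assessment of treatment effect) sets out the sample size for 100 patients. It states: "The probability is 70 percent that the study will detect a treatment difference at a two sided 10.0 percent significance level", given a true hazard ratio of 1.654. It lists these inputs: "the accrual period will be 36 months and the follow up period will be 6 months and the median time to event is 8 months". It concludes: "The total number of events will be 73". It does not give the method, the arm to which the 8-month median belongs, the allocation ratio or any allowance for losses.

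The observation window is fixed elsewhere:

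- Section 4.R, item 2 (Analysis of the primary endpoint) specifies an unadjusted log-rank test on time to first re-hospitalization or death. "Censoring will occur at the earliest date of any of the following occurrences, unless the subject has already experienced the primary outcome event"; the last item in that list is "180 days after randomization".
- Section 4.Q defines readmission and mortality "as a composite endpoint 180 days after randomization to roflumilast or matching placebo".
- Section 4.B has the study start before the patient's "discharge from the hospital and last for 194 days".

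**The concern.** An 8-month median is longer than the 180-day window (about 5.9 months). In the group with that median, fewer than half can have had an event when the clock stops, yet the plan expects 73 of 100. Accrual length matters to an event count only when early entrants are followed longer than late ones, and here nobody's primary-endpoint follow-up exceeds 180 days. The 36-month accrual term therefore looks as if it was counted as additional follow-up.

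This is the only numerical justification for n = 100. The feasibility and tolerance aims do not depend on it. The treatment-effect aim does: item 4 says the pilot is looking for a signal that would support a larger trial. A reader who accepts the stated power will take a non-significant result as stronger evidence against an effect than it is.

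**Working it through.** **Inputs.** From Section 4.R, item 4: N = 100, hazard ratio (HR) 1.654, two-sided alpha 0.10, power 0.70, accrual 36 months, follow-up 6 months, median 8 months. From item 2: censoring at 180 days = 180/30.4375 = 5.91 months. Assumed because not stated: exponential survival, 1:1 allocation (50 per arm), no losses.

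**Events required (Schoenfeld).** D = 4(z0.95 + z0.70)² / (ln HR)² = 4(1.645 + 0.524)² / (0.503)² = 74.3. In reverse, power = Φ(√D × ln HR / 2 − 1.645); at D = 73 this is Φ(0.505) = 0.693. So 73 events and 70% power agree with each other. The question is whether 73 events can occur.

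**Reproducing the plan's figure.** Take 8 months as the median of the higher-hazard arm. The hazards are ln 2/8 = 0.0866 and 0.0866/1.654 = 0.0524 per month. With uniform accrual over 36 months and everyone followed to month 42:

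P(event) = 1 − exp(−6λ)(1 − exp(−36λ)) / (36λ) = 0.818 and 0.671.

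Events = 50 × (0.818 + 0.671) = 74.5; power 0.701 (simulated log-rank 0.696, 20,000 runs). This is close to the stated pair.

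**Same inputs, 180-day limit.** P(event) = 1 − exp(−5.91λ) = 0.401 and 0.266.

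Events = 50 × (0.401 + 0.266) = 33.4.

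Power = Φ(√33.4 × 0.503/2 − 1.645) = Φ(−0.19) = 0.424 (simulated 0.424). Using 6.0 months instead of 180 days gives 33.8 events and 0.427.

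**Other readings of the 8-month median:**

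| 8 months is the median of | Events, common close | Events, 180 days | Power, 180 days | HR with 70% power, 180 days | Follow-up per patient for 73 events |
|---|---|---|---|---|---|
| higher-hazard arm | 74.5 | 33.4 | 0.42 | 2.20 | 19.6 months |
| geometric midpoint of the arms | 81.2 | 40.6 | 0.48 | 1.97 | 15.3 months |
| lower-hazard arm | 86.8 | 48.6 | 0.54 | 1.84 | 11.9 months |

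The detectable HRs let the event count change with the HR. For the first row, HR 2.195 gives 30.5 events, and 4(1.645 + 0.524)²/(ln 2.195)² is also 30.5.

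Conversely, 73 events by day 180 would need a median of about 2.4 months in the higher-hazard arm, equivalent to 4.0 months in the lower-hazard arm.

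**Check without the exponential assumption.** Before the median, fewer than half of an arm has had an event. With proportional hazards and 50 per arm, the ceilings are:

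- 8 months in the higher-hazard arm: 25 + 50 × (1 − 0.5^(1/1.654)) = 25 + 17 = 42 events, power about 0.50.
- 8 months in the lower-hazard arm: 25 + 50 × (1 − 0.5^1.654) = 25 + 34 = 59 events, power about 0.61.

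**Observed HR needed for p < 0.10.** exp(2 × 1.645/√D) is 1.77 at 33.4 events and 1.47 at 73.

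**The case against.** The strongest objection is that 33 events and 42% come from a model, not from the plan. The plan names no arm, survival distribution, allocation ratio or loss rate. Constant hazard is also doubtful here. An exponential with an 8-month median implies about 8% with an event by 30 days, whereas Section 1.B puts 30-day readmission at roughly 15% in most studies and cites 20.5% from a US database. A Weibull curve with the same higher-hazard-arm median and shape 0.5 to 0.7 gives 15% to 22% at 30 days, 36 to 38 events by day 180 and power of 0.44 to 0.46. This stands as a reason to quote a range. It does not rescue the stated figures, since even the shape-free ceilings fall short of 73 events and 70%.

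The origin of the 73 is inferred: the common-close model gives 74.5, and the plan does not describe that model. The conflict with 180-day censoring does not depend on the inference, which only selects the headline reading. That reading is the closest match of the three and fits the plan's aim of lengthening time to event.

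The HR of 1.654 may be a detectable effect solved from n = 100 rather than an expected one. The plan does not say. If so, the most useful correction is the detectable HR, which rises to about 1.8 to 2.2.

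Finally, this is a pilot. The plan already uses that to relax alpha to 0.10 and power to 0.70, and then states 73 events and 70% as properties of this study. The pilot label does not make those figures attainable.

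**Conclusion.** The concern holds. The event count and power in Section 4.R, item 4 contradict the censoring rule in item 2. Under exponential survival, 1:1 allocation, no losses and an 8-month median in the higher-hazard arm, the design yields about 33 events and 42% power, so an HR of 1.654 would be missed about 58% of the time rather than 30%. Across readings of the median the range is 33 to 49 events and 42% to 54% power. Losses to follow-up, which item 2 anticipates, would reduce these further. The exact replacement figures depend on those assumptions. The conclusion that 73 events and 70% power are out of reach needs only proportional hazards, equal allocation and the plan's own 8-month median.

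**What to change.** Recalculate Section 4.R, item 4 for fixed 180-day follow-up so that it agrees with item 2:

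- Remove the accrual term and the 73 events.
- State which arm has the 8-month median, and give the allocation ratio, survival assumption and allowance for losses.
- If the higher-hazard (placebo) reading is confirmed, report about 33 events and 42% power for HR 1.654 at two-sided 10%, with 70% power only for an HR of about 2.2. If not, use the matching row of the table (about 1.8 to 2.2 overall).
- Add that a non-significant pilot result has limited power to exclude an HR of 1.654.

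This changes SAP wording only; the endpoint, test and conduct stay as they are. The cost is a less favourable stated power. No extra patients are needed for a pilot. For comparison, keeping 70% power at HR 1.654 within 180 days would take about 74.3/0.334 ≈ 220 patients before losses.
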